The most complete approach to investigating AAGA would be to screen all eligible individuals with a standardised tool, then rigorously assess each potential report with further investigation, before reaching a consensus classification of the event against pre-established definitions of AAGA. This is exactly the methodology to be adopted by our DREAMY study, using Brice questionnaire as the screening tool, but adding structured follow up, where appropriate, to elucidate the nature of the possible AAGA experience and its consequences. By taking this approach the research team aim to produce the most comprehensive analysis of AAGA in obstetric patients to date.

5 Research Question

The DREAMY study aims to fulfil research implications 16.6 and 16.7 from the National Audit Project 5 (NAP5) Report, in relation to AAGA in the obstetric population. These implications are to “...define the incidence of AAGA as identified by the Brice questionnaire” [Research Implication 16.6, NAP5] and “to explore whether factors make obstetric patients more likely to report episodes of AAGA than the non-obstetric population” [Research Implication 16.7, NAP5].

There are three competing research hypotheses: that the incidence of Brice positivity in obstetrics is similar to that of the general population (~1:660), similar to Paech’s [Paech 2009] already reported incidence (~1:152) or that the ratio between “Brice positive” and spontaneous reporting is maintained with the general population (~1:19).

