12.2 Statistical analysis plan

12.2.1 Estimated sample size and expected recruitment

Aggregation of NHS hospital-level audit data collected by PLAN and data for Greater London from the Office for National Statistics [ONS 2014] and Health & Social Care Information Centre [HSCIC 2014] confirms an annual expected birth rate of approximately 150,000 per annum across the maternity units in the Greater London area. Direct data, collected by PLAN from these units, covering 209,982 deliveries indicates that 4,027 GAs were provided to facilitate maternal delivery over the same time period; this is equivalent to a GA proportion of 1.92% (95% CI 1.86% – 1.98%) for all deliveries.

Given the expected annual birth rate of approximately 150,000, we therefore expect approximately 2,880 GA deliveries (95% CI 2,685 – 3,075) over a given 12 month data collection period. Patients undergoing non-LSCS obstetric surgery under GA (e.g. manual removal of placenta) will also be eligible for inclusion: based upon the same audit data this is expected to increase the total number of eligible patients by a factor of 1.12 to 3,225 (95% CI 3008 – 3444) per annum.

We aim to recruit at least 70% of all eligible patients – equivalent to a point estimate of ~2250 included participants over 12 months. Some women will be ineligible to participate due to the inclusion criteria (e.g. must be English speaking). We also expect a proportion of eligible women to decline involvement and the total number of recruitment hospital sites to vary, hence the final included number of participants may be lower or higher than this point estimate.

This is a descriptive observational study with the intent of capturing data from as many eligible participants over a 12 month study period as possible. The power of the expected sample size to exclude the possibility of not detecting an incidence of “Brice positive” AAGA that is at least three times the incidence described in the overall surgical patient population (taken as 0.15% or 1:660 [Sandin 2000]) using an exact binomial test and one-sided α of 0.05 is 88%.

Analysis and post hoc power calculations will be taken at the 12 month threshold, with a view to potentially extending the study dependent upon the confidence interval width of the identified AAGA proportion and ability to make a statistically significant comparison between previously documented incidences for AAGA.

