No formal estimate is made for the sample size of the baseline comparator group of non-AAGA patients who will be undergoing PTSD screening at 30 days. A lack of clear evidence regarding PTSD prevalence in patients receiving general anaesthesia for obstetric surgery would make such estimations speculative. Therefore, sample size has been preferentially determined by operational issues and consideration of sample size of studies identified in a previous systematic review of post-natal PTSD [Anderson 2012].

12.2.2 *Primary endpoint analysis*

The proportion of obstetric GA patients reporting AAGA will be expressed using binomial confidence intervals and compared with established values (see above for rectification of sample size).

There are three competing hypotheses. First, that the event proportion of Brice positivity in obstetrics is similar to that of the general population (i.e. ~1:660). If so, then we expect ~4 patients (binomial 95% CI 1 – 10). Second, that our incidence of Brice positivity will be similar to Paech’s already reported incidence (i.e. ~1:152 [Paech 2008]). Then we expect ~15 (95% CI 8 – 25) patients. Third, that the ratio between “Brice positive” and spontaneous reporting as in the general population (i.e. 1:660 vs 1:19,000) is maintained for obstetric patients (i.e. ~1:19). Then we expect 118 patients (95% CI 98 – 141). These figures for each of the three possible outcomes will be compared using Fisher’s exact test or chi-squared testing to yield a definitive answer as to which is the most likely hypothesis of the three.

Because we are administering the Brice questionnaire during 0-24h following the index GA (i.e. as soon as possible after GA recovery), we expect to obscure those cases who may otherwise report spontaneously. In other words, we do not expect by our methods to detect spontaneous reporting as such, as the questions will already have been asked. It is possible that some few patients may telephone in after their discharge to report that they now recall AAGA, perhaps triggered by the study, but even that would not fulfil the criterion for spontaneous reporting. We plan to class any such cases as “triggered reporting” and analyse them separately.

Subgroup analysis of the AAGA proportion will be conducted for type and urgency of surgical procedure (including emergency LSCS), de novo conversion from regional anaesthesia to GA and for GA inductions using propofol vs. thiopental.

12.2.3 *Secondary endpoint analysis*

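### The promised definitive choice among 1:660, 1:152 and 1:19 cannot be guaranteed: a plausible range of counts would reject all three, and not rejecting 1:660 does not show similarity

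*Protocol*

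**What the plan says.** Section 5 (Research Question) introduces the benchmarks: "There are three competing research hypotheses: that the incidence of Brice positivity in obstetrics is similar to that of the general population" (about 1:660), or close to an earlier obstetric study (about 1:152), or scaled up by the ratio of Brice-positive to spontaneous reports (about 1:19).

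Section 12.2.1 gives the planned size as "equivalent to a point estimate of ~2250 included participants over 12 months".

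Section 12.2.2 first says that the proportion will be reported with binomial confidence intervals and set against established values. It then gives an expected count for each benchmark:

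- 1:660: "If so, then we expect ~4 patients (binomial 95% CI 1 – 10"
- 1:152: "Then we expect ~15 (95% CI 8 – 25) patients"
- 1:19: "Then we expect 118 patients (95% CI 98 – 141"

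It continues: "These figures for each of the three possible outcomes will be compared using Fisher’s exact test or chi-squared testing", and gives the purpose as "to yield a definitive answer as to which is the most likely hypothesis of the three".

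The section gives no margin for similarity, no likelihood or posterior comparison, and no rule for a result that fits none of the three. For this comparison it does not fix the significance level, the sidedness, or whether the test is one-sample or two-sample.

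**The concern.** A significance test measures how far the data conflict with one value. It does not rank several values, and it can reject every value on the list. Three isolated incidences between 1:660 and 1:19 leave wide spaces between them, so the tests may return no answer where the protocol promises a definitive one.

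The first hypothesis has a further difficulty. It is worded as similarity, "that the event proportion of Brice positivity in obstetrics is similar to that of the general population (i.e. ~1:660", and the only route to it through these tests is a non-significant result. With few events, such a result is also compatible with rates well above 1:660.

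At stake is the interpretation of the primary result. If none of the three fits, the plan does not say what will be concluded. If 1:660 is not rejected, a reader could be told that obstetric risk resembles general surgical risk when the interval allows several times that rate. Section 12.2.1 also lets a possible extension at 12 months depend partly on being able to make a significant comparison with earlier incidences, so the same reasoning could affect conduct.

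**Working it through.** **Inputs.** n = 2,250 (section 12.2.1); benchmarks 1/660, 1/152 and 1/19 (sections 5 and 12.2.2); earlier obstetric study 5/763 (section 4, Background). Assumption: two-sided 5%, to match the 95% intervals.

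**1. Reproducing the printed figures.** Expected count = 2,250 × p, giving 3.4, 14.8 and 118.4. Exact (Clopper-Pearson) 95% limits for 4, 15 and 118 out of 2,250, multiplied by 2,250, are 1.1–10.2, 8.4–24.7 and 98.1–140.6. These match the printed 1–10, 8–25 and 98–141. The printed ranges overlap at 8–10 and leave 26–97 uncovered.

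**2. Counts that retain each benchmark.** Exact one-sample, equal-tailed rule: retain p at count x if P(X ≤ x) and P(X ≥ x) both exceed 0.025, with X binomial(2,250, p).

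| Benchmark | Lower edge | Upper edge | Retained |
|---|---|---|---|
| 1:660 | P(X ≤ 0) = 0.033 | P(X ≥ 7) = 0.058; P(X ≥ 8) = 0.023 | 0–7 |
| 1:152 | P(X ≤ 7) = 0.020; P(X ≤ 8) = 0.041 | P(X ≥ 23) = 0.028; P(X ≥ 24) = 0.017 | 8–23 |
| 1:19 | P(X ≤ 97) = 0.022; P(X ≤ 98) = 0.027 | P(X ≥ 140) = 0.0255; P(X ≥ 141) = 0.021 | 98–140 |

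Counts of 24–97 reject all three, as do counts above 140. As incidences, 24/2,250 is 1:94 and 97/2,250 is 1:23. The minimum-likelihood exact test and the one-sample chi-squared test give 23–97.

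**3. Other readings of the test.** A two-sample Fisher test against 4, 15 and 118 out of 2,250 retains 0–12, 6–28 and 90–150. The gap becomes 29–89, and counts of 6–12 fail to separate 1:660 from 1:152. A Fisher test against the earlier study's actual 5/763 does not reject any count from 4 to 36.

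**4. Is the gap plausible?** The exact 95% interval for 5/763 is about 1:469 to 1:66. Its upper end passes 1:94, where the gap begins. Probability of a count in the gap:

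| True incidence | P(24 ≤ X ≤ 97), one-sample | P(29 ≤ X ≤ 89), two-sample Fisher |
|---|---|---|
| 1:100 | 40% | 10% |
| 1:75 | 89% | 60% |

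**5. Non-rejection of 1:660.** Seven cases retain 1:660, yet the exact 95% interval is 1:799 to 1:156; the upper limit is 660/156 = 4.2 times the benchmark. If the true incidence is 1:330, twice the benchmark, P(X ≤ 7) = 63%, so the test fails to reject 1:660 in about five trials in eight.

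**6. Strength of evidence at the boundary.** At 7 cases the one-sample tests retain 1:660; at 8 they retain 1:152 instead. At 8 cases the binomial likelihood favours 1:152 over 1:660 by only 1.4 to 1.

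**The case against.** The strongest reply is that this is an estimation study. The research question, primary aim and primary endpoint all concern a proportion, section 12.2.1 describes the study as descriptive, and section 12.2.2 opens with the binomial interval. That stands. A reader might infer that the whole primary analysis is a choice among three hypotheses and could return nothing. The documents do not support that: with 24–97 cases the proportion and its interval would still be reported and would visibly exclude all three benchmarks.

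Three further stronger readings also fail.

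- *The tests would pick the wrong hypothesis.* With fixed-rate tests, no count is compatible with two benchmarks, and wherever one is retained it is the best supported of the three. If one benchmark were exactly true, these tests would usually identify it.
- *The plan commits to declaring similarity from a non-significant result, or to choosing a rejected hypothesis.* Neither is written. The promised answer invites both, and nothing in the section rules them out. The interval, and the plan to consider extension according to its width, limit the risk in part.
- *Even the expected 4 cases would not exclude a threefold rate.* This is a knife-edge: the upper limit is 1:219.997 against a threefold rate of 1:220. At 3 cases the upper limit is 1:257 and threefold is excluded. The 7-case example does not have this weakness.

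It is also fair that 24–97 follows from an assumed form of test and is not a figure fixed by the protocol. The limits move with the form, but a gap remains under both the one-sample tests and the two-sample Fisher test against the expected counts.

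What survives is narrower: the sentence states a conclusion that the named tests cannot guarantee. Because the protocol makes the claim itself, a separate analysis plan that filled in detail would not remove it.

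**Conclusion.** The concern holds for the interpretive claim in section 12.2.2, not for the estimate. Fisher's or chi-squared tests of three isolated incidences cannot guarantee a definitive choice of the most likely one. At 2,250 participants, and assuming exact one-sample, two-sided, equal-tailed 5% tests, 24–97 cases or more than 140 would reject all three. The two-sample Fisher form gives a gap of 29–89 and adds an ambiguous zone at 6–12. The protocol's own printed ranges already show both a gap and an overlap.

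The gap lies partly within what the earlier obstetric data allow. How likely it is depends on the true incidence, which is unknown, and on the form of test. At the low end, retaining 1:660 is weak evidence of similarity, because no margin is set and a doubled rate would go undetected more often than not.

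The planned proportion and confidence interval are sound and unaffected.

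**What to change.** In section 12.2.2, replace the sentence that promises a definitive answer with text such as:

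> The incidence and its exact 95% confidence interval are the primary result. We will state which of the three benchmark incidences lie inside the interval. If none does, we will conclude that none of the three holds. Non-significance against 1:660 will not be read as similarity.

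Nothing is lost relative to fixed-rate testing: a benchmark lies inside the exact interval exactly when the equal-tailed exact test retains it. Binomial likelihood ratios between the benchmarks could be added as a measure of relative support, but they are optional.

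The cost is a few sentences and no new data. The downside is a less categorical conclusion.

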All suspected AAGA patients will also be offered the PCL-5 PTSD checklist ([Appendix 5](#)) at day 30, 3, 6, 9 and 12 months following the index anaesthetic episode. The checklist will be administered via telephone by the DREAMY Research Team (although written forms or face-to-face will be provided if requested). During first administration of the PCL-5 checklist additional target information will be obtained using a structured and multi-dimensional questionnaire on the woman's self-reported mental health history, infant's health status and psychological experiences in the gravidic-puerperal cycle. Question domains have been derived from known risk factors for developing PTSD during the post-natal period [Andersen 2012] and will also be asked to the comparator sample of 300 non-AAGA patients collected during the early phase of the study (see [Section 6.5](#)).

An extended AAGA follow up will occur during the 3 month PTSD follow up episode, with a view to investigating the nature of local clinical follow up received by patients and how the AAGA episode has impacted on attitudes towards future anaesthetics and post-natal experience (see [Appendix 7](#) for questions used).

[figure not shown]

Figure 4. Suspected AAGA Follow Up flowchart

10 Data management and quality assurance

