12.1.2 Secondary endpoints

The secondary endpoints are:

1. Descriptors of anaesthetic, surgical and patient factors associated with AAGA
2. 3, 6, 9 and 12 month results of the Post-Traumatic Stress Disorder Checklist (PCL-5), for patients with confirmed AAGA. This will be compared with PTSD incidence in the initial cohort of non-AAGA participants.
3. Qualitative description of the experience of AAGA undergone by obstetric patients.

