For secondary outcomes of interest, data will be presented as a number or percentage; mean and standard deviation (SD) for normally distributed data and median and interquartile range (IQR) for non-parametric data, with 95% confidence intervals (CI). Significance of associations with anaesthetic, surgical and patient factors will be tested using relevant measures of correlation. If sufficient AAGA events are identified, then a multivariable regression model will be used to evaluate the independent association of specific anaesthetic episode variables with AAGA, with results expressed as odds ratios (ORs).

Post-Traumatic Stress Disorder Checklist (PCL-5) results will be expressed as a total symptom severity score (range = 0-80), obtained by summing the scores from each of the 20 checklist items. PCL-5 questions are grouped into 4 domains referring to different symptom criteria: 5 questions refer to symptoms of re-living (cluster B), 2 to avoidance behaviour (cluster C), 7 to emotional blunting (cluster D) and 6 to symptoms of hyper-excitability (cluster E). Symptoms are considered significant when the person scores 2 or more on the item. Women will be considered positive on the PCL-5 when they have at least 1 significant symptom for cluster B, at least 1 for cluster C, at least 2 cluster D items and 2 cluster E [Blevins 2015, National Centre for Posttraumatic Stress Disorder]. PTSD prevalence rates will be estimated for the entire sample and certain subgroups, including AAGA and non-AAGA patients. Results will be expressed with the respective 95% confidence intervals. Fischer's exact test will be used to test the homogeneity of prevalence rates in the subgroups.

Case descriptions of the experiences of AAGA undergone by patients with AAGA will be presented in anonymised format. The phase of anaesthesia/surgery when the AAGA event occurred, alongside possibility contributory, causal or mitigated factors, will be described where possible.

13 Direct access to source data

The Investigator(s)/institution(s) will permit study-related monitoring, audits, REC review, and regulatory inspection(s), providing direct access to source data/documents. Study participants are informed of this during the informed consent discussion. Participants will consent to provide access to their medical notes.

14 Ethics and regulatory requirements

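### The PCL-5 total score is collected but not compared between AAGA and non-AAGA women; the only named test is Fisher's on a yes/no result, which costs power if AAGA cases are few

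*Protocol*

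**What the plan says.** Section 12.2.3 describes two ways of using the PCL-5.

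- **A score.** The results are to be "expressed as a total symptom severity score (range = 0-80), obtained by summing the scores from each of the 20 checklist items". This is a commitment to report. No between-group test of the score is named.
- **A yes/no result.** An item counts as a significant symptom when scored 2 or more, and a woman is positive with "at least 1 significant symptom for cluster B, at least 1 for cluster C, at least 2 cluster D items and 2 cluster E". This is a symptom-cluster rule, with no threshold on the total.

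The comparison is then set out for the yes/no result only: "PTSD prevalence rates will be estimated for the entire sample and certain subgroups, including AAGA and non-AAGA patients", with 95% confidence intervals, and Fisher's "exact test will be used to test the homogeneity of prevalence rates in the subgroups". Section 12.1.2 frames it the same way. It lists PCL-5 results at 3, 6, 9 and 12 months for confirmed AAGA and adds "This will be compared with PTSD incidence in the initial cohort of non-AAGA participants".

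The group sizes come from elsewhere. Section 12.2.2 gives three scenarios for Brice-positive women: about 4, about 15 and 118. For the lowest it says "If so, then we expect ~4 patients (binomial 95% CI 1 – 10". Section 6.5 ends collection of the comparator sample once at least 300 women have responded, and those women complete the PCL-5 at day 30 only. Section 12.2.1 gives no formal size for that group and calls any estimate of PTSD prevalence speculative.

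The Appendix 6 risk-factor questions go to both groups at day 30. Of these, section 9.3 says: "Question domains have been derived from known risk factors for developing PTSD during the post-natal period".

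**The concern.** In two of the three scenarios the AAGA group is very small, so its size limits what the comparison can show. Reducing 20 graded items to one yes/no answer discards information exactly where there is least of it. Fisher's test is also conservative with such sparse counts, and it cannot use the Appendix 6 factors.

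The psychological consequence of AAGA is a stated secondary aim (section 5.2). If the only test named for it is a weak one, a real difference in symptoms may go undetected although the data that could show it are already on file. A score comparison added after the data have been seen would be open to the charge of being chosen for its result.

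**Working it through.** **1. The plan's case numbers.** With N = 2250:
- 2250/660 = 3.4 (plan: about 4)
- 2250/152 = 14.8 (plan: about 15)
- 2250/19 = 118.4 (plan: 118)

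Exact (Clopper-Pearson) limits, scaled to 2250, are 1.1-10.2 for 4 cases, 8.4-24.7 for 15 and 98.1-140.6 for 118. They match the plan's 1-10, 8-25 and 98-141. These are Brice-positive counts, whereas section 12.1.2 compares confirmed AAGA, which may be fewer. In the earlier obstetric study 2 of 763 were definite, and 2/763 × 2250 = 5.9.

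**2. One cell by hand.** Assumptions, none from the protocol: two-sided 5%, n0 = 300, comparator positivity p0 = 5%, and scores shifted uniformly by d = 0.8 SD on a normal scale.
- AAGA positivity: p1 = Φ(Φ⁻¹(0.05) + 0.8) = Φ(−0.845) = 19.9%.
- Fisher's test, by exact enumeration: 49% power with 15 cases, 18% with 4.
- t-test on the score, 15 cases: noncentrality d√(n1·n0/(n1+n0)) = 0.8√(4500/315) = 3.02. Power ≈ Φ(3.02 − 1.97) = 85%. Loss from using Fisher: 36 points.
- t-test on the score, 4 cases: 0.8√(1200/304) = 1.59. Power ≈ Φ(1.59 − 1.97) = 35%. Loss: 17 points.

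Over p0 = 3-20% and d = 0.5-1.0 the loss is 3-34 points with 4 cases and 13-47 points with 15.

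**3. Item-level simulation.** Twenty ordinal items were scored with the protocol's own cluster rule, with 300 comparators and AAGA positivity set to 21%. Fisher's test was set against a permutation test on the mean total, with 15 cases:

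| Comparators positive | Cases affected | Fisher | Permutation | Gain (points) |
|---|---|---|---|---|
| 3.5% | all | 65% | 98% | 33 |
| 3.5% | 41% | 65% | 87% | 22 |
| 3.5% | 25% | 64% | 82% | 18 |
| 6% | all | 46% | 84% | 38 |
| 6% | 41% | 47% | 74% | 27 |
| 6% | 25% | 47% | 67% | 20 |
| 10% | all | 26% | 51% | 25 |
| 10% | 41% | 27% | 44% | 17 |
| 10% | 25% | 26% | 42% | 16 |

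With 4 cases the gain was 13-42 points. Under the null, Fisher's size was 2-3% and the permutation test's 4-5%, so the gain is not bought with extra false positives. A separate simulation with 15 cases gave 24-66% for Fisher and 41-95% for the permutation test. Taken together, the gain is roughly 10-45 points at 4 to 15 cases.

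**4. Where the gain shrinks.**
- *Harm in a subset, latent-normal model.* Let 21% of 15 cases be affected by 2.5 SD, with p0 = 5%. The mean shift is only 0.21 × 2.5 = 0.53 SD, yet most affected women cross the threshold: Φ(−1.645 + 2.5) = 80%. Fisher has 52% power and the t-test 49%. With 41% affected the figures are 90% and 89%. The gain is gone. The same scenario simulated at item level still gave 20-25 points (21% affected) and 7-19 points (41% affected), so the answer depends on the model.
- *118 cases.* At item level the gain is 0-2 points unless comparator positivity is near 10%. There, 21% against 10% is a shift of only Φ⁻¹(0.21) − Φ⁻¹(0.10) = −0.81 + 1.28 = 0.48 SD. The normal model, with comparators at 5-10%, loses 16-28 points at d = 0.5 and about none at 0.8 or more.

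**The case against.** The other side has four fair arguments.

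1. *The study is descriptive and the endpoint is PTSD incidence.* Fisher's test is the standard choice for sparse counts, and intervals are promised. This stands as a reason to keep the prevalence comparison. It is no reason to leave the score uncompared.
2. *A further test of a secondary outcome may be in a statistical analysis plan that is not shown.* This is possible, and nothing in section 12.2.3 forbids it. But the protocol is not silent: it names the outcome to be compared and the test.
3. *The size of the loss rests on assumed rates.* This stands. The 21% echoes 3 of 14 obstetric cases in section 4, but those women had new psychological morbidity in a national audit, which is not PCL-5 positivity.
4. *Under the third scenario there is little to gain.* This stands, except with comparator positivity near 10% or a modest shift.

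A reader might go further and infer that the plan expects 10 to 15 cases, that positivity is a cut of the 0-80 total, or that a real difference would probably be reported as non-significant. The documents support none of these. The scenarios are about 4, about 15 and 118, with none preferred. Positivity is a cluster rule. Whether a difference would be missed depends on case numbers and rates that the protocol does not give.

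**Conclusion.** The point holds in a limited form. The protocol collects a graded score and names a between-group test only for a yes/no reduction of it. With about 4 or 15 AAGA cases and at least 300 comparators, this costs roughly 10-45 percentage points of power in item-level simulations assuming 3.5-10% comparator positivity and about 21% AAGA positivity.

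That range is conditional and does not cover every plausible case. It can fall to about zero under a latent-normal model with harm in a subset, and it is small with 118 cases unless comparator positivity is near 10%. Nor do the results show that the prevalence comparison is wrong or should be demoted, since section 12.1.2 names it as the endpoint. This is a cheap improvement to a secondary analysis.

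**What to change.** In section 12.2.3:

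- Add a pre-specified comparison of the mean day-30 PCL-5 total between AAGA and non-AAGA women, stating whether AAGA means Brice-positive or confirmed. Day 30 is the only time point at which comparators are measured.
- Give a permutation p-value and a confidence interval suited to a very small group, for example by inverting the permutation test (which assumes a common shift). Avoid a percentile bootstrap: in one simulation, not repeated, its 95% interval covered about 72-83% of the time with 4 cases and 88-91% with 15.
- Compare means and not ranks. With harm confined to a subset and 10-15 cases, Fisher's test beat Wilcoxon by 16-26 points under the latent-normal model.
- Keep cluster-rule prevalence, with exact intervals and Fisher's test, beside it.
- If case numbers allow, add a linear model of the total adjusted for a few Appendix 6 factors, such as prior psychological disorder, perinatal outcome and neonatal ICU admission.

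The cost is a wording change and an analysis of data already collected. The small downside is one more secondary comparison, in score points, to report beside prevalence.
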